### Work package 2: Service delivery and fidelity

*Rationale:* The NHS Low Calorie Diet programme specification is based on the protocols from two underpinning trials[11, 12]. To test whether the outcomes of these trials can be replicated within larger more diverse populations it is important that the NHS Low Calorie Diet pilot is delivered with fidelity to the programme specification. This is important because the existing trials were based on a single provider and used only one behaviour change delivery model (one to one support). As the NHS Low Calorie Diet will be trialling the use of different providers, and two additional behaviour change delivery models (group and digital support), an evaluation of treatment fidelity across different providers and delivery models is essential.

*Overview of methods*: This work package will use a combination of documentary review, session observations, interviews with NHS support staff, and provider focus groups to answer RQs: 1-4.

The methods will be framed using the Health Behaviour Change Consortium NIH-BCC fidelity domains [30] (with a-c addressed in WP2 and d-e addressed in WP3):

- (a) Study design is the intervention congruent with relevant theory and best practice?
- (b) Training have practitioners been properly trained to deliver the intervention?
- (c) Delivery has the intervention been delivered as designed?
- (d) Receipt do patients understand the intervention and perform key skills during delivery?
- (e) Enactment do patients perform relevant skills in real life setting?

### Research questions WP 2.1 – Study design:

- What are the theoretical principles, behaviour change components, content and mode of delivery of the programme, and how do these vary across sites and providers? [RQ1]

### Methods:

Documentary review: We will collect information on wider support services (e.g. local care pathways, services linked to the NHS Low Calorie Diet programme, local Low Calorie Diet training programmes, incentivisation schemes and communications packages, as well as other locally available weight management and diabetes services) and the impact of COVID-19 (e.g. adaptation plans and impacts on wider support services) from each pilot site locality lead (who will be identified by NHSE). We will also collect the NHS Low Calorie Diet service specifications, training manuals, session content, and marketing materials used by each service provider (four providers have been commissioned – with two different providers for each delivery model). We will also ask the provider from each pilot area to complete the standardised reporting of lifestyle weight management interventions to aid evaluation (STAR-LITE) template[31] (which has been adapted to include additional questions to assess the impact of COVID-19 on service delivery, record resource use and unit costs for the economic evaluation, capture digital and remote delivery implications, and strategies used to

mitigate against digital inequalities). The STAR-LITE template will be completed every year by each service provider, in order to capture any year on year changes to service provision. The STAR-LITE survey will be made available electronically via Qualtrics surveys, and will facilitate the standardised reporting of intervention referral, delivery, components, and costs which will be used to 1) support a primary analysis of key intervention features (including behaviour change content, underpinning theory and delivery) across providers, and 2) evaluate adherence to the national programme specification.

*Analysis:* The output from the STAR-LITE survey and documents collated will be analysed using the documentary review methodology informed by Bowen[32], and will support WP4 and 5, and help inform the initial programme theory.

Research questions WP 2.2 – Training and delivery:

- To what extent does the staff training delivered by each provider apply behaviour change theory and content, and how does this vary across sites and providers? [RQ2]
- To what extent is the NHS Low Calorie Diet delivered with fidelity to the specification as set out by NHSE? [RQ3]
- What are provider and NHS support staff experiences of the service, and what do they perceive to be the key barriers and facilitators to effective delivery, integration and normalisation into routine care? [RQ4]

### Methods:

*Behaviour change coding:* Each providers' training manuals will be coded against Behaviour Change Technique taxonomy (v1)[33], and behaviour change theory using Michie & Prestwich's Theory Coding Scheme[34], aligning the methodology with that used for the evaluation of the National Diabetes Prevention Programme[35, 36]. This will be undertaken in duplicate, and used to assess the extent to which training coheres to the guiding behaviour change theory and content, and how this varies across providers.

*Face to face session observations (currently delivered remotely):* We will work with each service provider delivering one to one and group programmes to purposively select two delivery streams to observe from start to finish. Two providers are delivering the one to one, and two providers are delivering the group programmes. As there are 21 active sessions in both the one to one and groups sessions, this will result in a total of 168 observations (providing consent is gained from the staff lead and participants before each session). This will provide a longitudinal insight into delivery across different populations and delivery models. Descriptive non-participatory observations[37] will involve detailed field note taking to assess the behaviour of the delivery staff and participant interactions, during a routine programme delivery session. Observations will be conducted remotely by two experienced qualitative researchers who have experience of session observations and have been trained in coding Behaviour Change Techniques.

*Analysis:* Field notes (but not audio recordings) will be taken, entered into NVivo and used as part of the data. Fidelity will then be assessed by comparing observations to a fidelity checklist that will be developed from the behaviour change coding, formal service specification and service provider training manual/session content and STAR-LITE responses.

*Digital session observations:* As the active components of the digital programme are delivered almost entirely via digital media, digital service providers (n=2) collect data on the amount, frequency, duration and usage of the programme. We will therefore ask providers to share this data, alongside access to the programme content, in order to assess fidelity and behaviour change techniques used. We anticipate collecting the following data (in line with the methodology used for the National Diabetes Prevention Programme evaluation protocol https://fundingawards.nihr.ac.uk/award/16/48/07):

- Page views (with reference to behaviour change technique content mapped out by prior work)
- Number, time and date stamps of pages above

• Links clicked, data inputted and downloaded (i.e. to ascertain whether data has been inputted, e.g. a food diary entry, or whether a user has clicked through to use another component of the intervention, e.g. a live chat with health coach). NB this is assess usage data not personal content.

We will work with providers to ensure an opt-out consent process is in place for sharing usage data by: 1) reviewing existing terms and conditions and consent statements that service users complete when registering to take part in the digital Low Calorie Diet programme, and 2) revising consent statements where necessary in conjunction with the provider. Once an agreed opt-out consent process is in place, we will ask providers to identify a cohort of service users which will be followed for the duration of the programme (12 months). We expect this cohort to be identified as all new registrants with the digital programme for one month for each of the 2 providers. We will ensure that the data transferred to Leeds Beckett University from the providers is anonymised and does not contain any personally identifiable data. Providers will be specifically requested to undertake the following:

• Remove any personally identifiable data (name, contact details, date of birth, medical records, IP address)

• Remove any address details leaving only the first 3 letters of the postcode, which will allow us to assess the geographical spread of the usage data we obtain

• Review any free-text entries from service-users that risk sharing personally identifiable data

• Data quality assurance

We will request that providers encrypt the data files using an AES256 compliant encryption mechanism such as 7-zip. It will then be sent to Leeds Beckett University via the secure encrypted, password protected transfer system ZendTo.

Data files will be stored on the high security (NHS IG toolkit compliant server provided by Leeds Beckett University IT). We will request providers transfer data to us on a monthly basis using this process.

*Analysis:* We plan to use the AMUSED (Analyzing and Measuring Usage and Engagement Data) framework for evaluating the digital interventions[38]. This framework comprises three stages: 1) familiarisation with the intervention and its relationship with the captured data, 2) identification of meaningful measures of usage and specifying research questions to guide systematic analyses of usage data, and 3) preparation of datasheets and consideration of available analytical methods with which to examine the data. We will identify core BCTs (e.g. goal setting, action planning, self-monitoring, feedback, reviewing goals, problem solving and others mentioned in the intervention specification). We will code whether the BCT is present in the intervention (yes/no) and we will code whether users engaged with that specific BCT (yes/no). We will also report specific BCTs and key intervention features which were (1) offered to users, and (2) which users effectively engaged in, as will be conducted in the face to face session observations.

Service provider focus groups: Following ethical approval service providers will be invited to contribute to a focus group. We will aim to recruit a convenience sample of 13 focus groups with between 6-8 participants per group [39] (NB given the different delivery models, and some providers covering more than one pilot site, these focus groups will be organised to capture insights from key frontline staff members across the different service provider and delivery areas). Focus groups (which will be held virtually using video conferencing) will provide insight into providers experiences, and any shared barriers, facilitators and redundancies regarding implementation across different pilot areas, populations, and delivery models (including the impact of COVID-19, and any problems encountered with the referral process).

*NHS support staff interviews:* We will interview a convenience sample (n=10, one from each pilot area) of the NHS locality staff (i.e. those involved in mobilising the programme). We will aim to interview the locality lead within each pilot site during the first and second year of the programme, to examine how mobilisation, referral mechanisms, communications, training and incentivisation was initiated and developed during the roll out (total interviews n=20). We will also interview a purposive sample (n=20) of NHS staff responsible for referring and supporting patients on the programme, in order to capture insights from GP practices that have experienced referral challenges and successes within each of the pilot areas. All NHS staff interviews will be

conducted within 30-60 minutes and be undertaken one-to-one over a telephone or video call. These interviews will assess experiences and views of the programme from NHS support staff perspectives, including their insights on which patients may be excluded from care (i.e. do not engage with the health care system), which patients receive a conversation about the programme but decline a referral, the local management of patient referrals, staff training, patient centred care, the impact of COVID-19 and any additional indirect costs associated with the programme. We have costed in gift vouchers to help incentivise participation within NHS referral staff.

*Analysis:* All interviews and focus groups will be guided by a topic schedule informed by the research questions, patient group insights, and the mechanisms, context and outcomes defined by the realist approach and normalisation process theory (NPT). NPT comprises of four main concepts: coherence, cognitive participation, collective action and reflexive monitoring, and seeks to illuminate the processes by which staff normalise a new practice [27, 40, 41]. Using NPT will inform the staff interview/focus group question guides. As with the realist approach, NPT can be used across the life cycle of a project to guide and frame core issues. Thus, both approaches will be used at the initial stages of the project to offer direction and clarity to lines of questioning and will also provide a framework for data analysis.

All interviews and focus groups will be conducted remotely and digitally audio-recorded, and transcribed verbatim with consent of each participant. Each transcript will be checked for accuracy by the researcher who conducted the focus group or interview. NVivo software will be used to aid the data organisation and analyses. Two researchers will independently review a sample of transcripts to formulate codes. Codes will be inductively sorted into potential themes and relevant data extracts collated within identified themes[42, 43]. Thematic networks will be constructed to facilitate the structuring, description and interpretation of the themes[44, 45]. Within themes, case-ordered matrices (from interviews and focus groups) will be constructed according to variables of interest. This case-ordering will enable examination of differences across cases, between delivery modes, and/or different stakeholder groups[45]. Themes will then be built into an explanatory model to demonstrate how various factors might influence successful implementation of the intervention[45].

### Work package 3: Patient experience and inequities

*Rationale:* The experiences of patients eligible for the NHS Low Calorie Diet programme, as well as those delivering it (WP2) are critical to its success. However, previous research has demonstrated that sociodemographic factors can impact upon a patients' experience of living with T2D[46] and can influence Low Calorie Diet success[47]. The NHS Low Calorie Diet programme is based on evidence from two UK trials[11, 12], providing data on patient groups that were less diverse than the general population eligible for the NHSE Low Calorie Diet in England. It is therefore imperative that this evaluation comprehensively understands the experiences of patients sampled from diverse socio-demographic backgrounds and provides insight into any socio-demographic variation in programme uptake, compliance, adherence and success across the three different delivery models. This component of the evaluation is critical in ensuring: 1) the programme addresses the health inequalities that are prevalent across England[48], in particular the inequalities in obesity and diabetes prevalence relating to ethnic group and socio-economic status; and 2) providers are fulfilling their legal obligation to provide equality of opportunity across all protected characteristics[49]).

*Overview of methods:* This WP will use a combination of complementary stages, underpinned by a pluralistic approach, which include cross sectional and longitudinal participant surveys, with in-depth insight provided by cross sectional and longitudinal interviews using visually represented participant journeys gained through adapted photovoice methods. A longitudinal approach is deemed critical given the chronic relapsing nature of obesity, and the difficulties in long term weight loss maintenance[50]. These findings will be integrated with the quantitative process and outcome data from NHSE, to help examine the context-mechanism-outcome configurations and answer the following research questions.

Research questions WP3.1 - Patient receipt and enactment

- To what extent is the content of the NHS Low Calorie Diet understood and carried out by patients? [RQ5]

### Research questions WP3.2 - Patient experiences across socio-demographics and delivery models

- Do socio-demographic characteristics (such as socio-economic status, sex, ethnicity, start BMI, duration of diabetes) influence access, uptake, compliance and success on the NHS Low Calorie Diet programme, and does this vary across the different (one to one, group or digital) behaviour change delivery models?
   [RQ6]
- What aspects of the service work and do not work, for whom, in what context, and why? [RQ8]
- If effective, how can the service be improved in the future, to enhance patient experience and ensure any inequities are addressed? [RQ9]

### Stage 1: Programme wide cross sectional and longitudinal patient survey.

A short (~20minute) participant survey will be developed for each stage of the programme (baseline, end of TDR, end of food reintroduction, end of maintenance and withdrawal). These surveys will be co-developed with end users, drawing together the realist evaluation and NPT approaches to collect a qualitative overview of patient understanding (coherence, cognitive participation), enactment (collective action) and experiences of the programme (reflexive monitoring), in addition to supplementary quantitative data (not currently collected by the NHS minimum dataset, but required to support WP4 & WP5) which will: 1) help understand influencers of uptake, withdrawal, retention and compliance, and how these may vary by socio-demographic factors and delivery model; 2) provide an overview of participant experience and expectations. The survey will be co-developed and tested with our PPI group and current NHS Low Calorie Diet service users to ensure it is acceptable to service users, will provide data that will be useful to participants, and gives rise to participant insights that will further enhance interpretation of the staff interviews (WP2) and the NHSE quantitative data. In order to align with the Diabetes Prevention Programme evaluation, tier 2 weight management minimum dataset and PPI group recommendations, the survey includes a wellbeing assessments (WEMWS[51] and EQ-5D[52]), emotional eating[53], binge eating[54] and activity assessment (Sport England single item question). This data will then be anonymously linked (via a unique referral ID) to the sociodemographic, process and clinical outcomes data collected by NHSE as part of the Low Calorie Diet minimum dataset. The qualitative (free text) questions will explore non-clinical patient centred outcomes, cost, barriers, facilitators, additional weight control practices, the impact of COVID-19 and service improvements. The survey will be available via a secure encrypted online survey. Participants will be asked to provide contact details (phone or email address) in a separate survey (not linked to the participant survey) if they wish to take part in the prize draw and/or would be interested in receiving information about other research opportunities within the study. Data will also be collected cross sectionally for any participants who do not wish, or are unable to complete, the survey at every time point.

Following receipt of ethical approval, we will ask each service provider to send the Participant Information Sheet (PIS) (complete with their unique referral ID) which includes a link to the survey and freephone number to complete the survey over the phone, at the following time points:

- Baseline survey to be completed between the initial assessment and the first week of the TDR phase.
- End of TDR survey to be completed at during the last week of the TDR phase and first week of the food reintroduction phase.
- End of food reintroduction survey to be completed during the last week of the food reintroduction phase and first week of the maintenance phase.
- Maintenance phase to be completed during the last two weeks of the maintenance phase.
- Withdrawal survey to be sent to all participants at the point of withdrawal.

<sup>4 PowerPoint Presentation (sportengland.org)

<sup>5 Security Statement // Qualtrics

A freephone number will be established for patients who would rather complete the survey verbally or in another language, to enable participation irrespective of literacy, language, visual ability or internet access (call handlers (with assistance of a translator where required) will complete the online survey on behalf of the participant). We will work with the PPI group to develop a short film about the survey to help raise awareness and survey completion. The PIS and supporting links and phone number, will also be available for participants to access via the Re:Mission study website (www.remission.study). A prize draw of 12x£50 gift vouchers will be made available to incentivise participation, with a prize draw organised and publicised by the study PPI group (4x prize draws per study year). We anticipate an initial survey response rate of around 30% (~1,500 of the 5,000 anticipated patients) based on an uptake of 33.1% observed in the most recent GP patient survey[55]). NB the participant survey will also be distributed to the additional 11 pilot sites that will operationalised from January 2022, which will expand the available recruitment pool.

*Analysis*: Descriptive and where appropriate inferential statistics will be used to assess any numerical and categorical data in either Excel or SPSS, and free text responses will be synthesised and assessed for emerging themes using Scaled Insights Behavioural Artificial Intelligence software.

### Stage 2: Case study: In-depth patient insights.

Of the participants who express an interest in taking part in this stage of the research (either via the study website, participant survey, or recruited by the service provider), we will undertake maximum variation sampling[56], to gain a range of different perspectives by recruiting people from a variety of backgrounds and experiences from across the three delivery models. This form of sampling is designed to explore multiple facets of a problem and investigate issues holistically[56]. Sampled patients will be invited to take part in a 60 minute one to one telephone interview, undertaken at the end of each phase of the programme (12,18 and 52 weeks), replicating the longitudinal gualitative approach undertaken as part of the Counterbalance study[57] and [name][58]. The purpose of the interviews is to provide in-depth insights into what works, for whom, in what context and why (collecting patient data to assess the mechanism, context and outcomes of the programme). We anticipate recruiting approximately 66 participants - a minimum of six participants who did not start or withdrew from the programme, and at least 30 participants (10 from each delivery model) who start the programme and will be followed up over time. When recruiting six participants who did not start or withdrew from the programme we will aim to sample equally to three groups: those discharged before starting total diet replacement, those discharged during total diet replacement, and those discharged after completing total diet replacement. We will aim to over sample in anticipation of some drop out. The interviews from participants who do not complete the longitudinal interviews will be assessed cross sectionally, additional cross sectional interviews may also be undertaken to explore any key emerging themes in more detail. The interviews will be undertaken using a semistructured interview guide informed by the realist approach, research questions, photovoice materials (where used) and co-production process (to ensure data enriches the NHSE data) and insights from the survey responses. It is anticipated that the interviews will develop insight into patient expectations and experience of the service, and where appropriate: the reason for not engaging, unexpected or unintended outcomes, what was liked most and least about the service, interaction with other services, confidence in implementing the contents, greatest challenges and successes, views on how the service was delivered, impact of the service on the wider family and social networks, resultant lifestyle changes and achievements, and further explore the context such as the impact of cultural differences, the effect of family and social networks and / or the place of food in the daily lives of participants. The interviews will be supported by our socio-demographically diverse PPI group, who will also be trained in undertaking interviews, so participants can opt to be interviewed by a trained PPI member alongside the study researcher, in recognition of the benefits of having community members as researchers. Prior to each interview participants will also be invited to undertake a 24hr dietary review (using myfood24), either with the researcher after completing the interview or independently beforehand, to track more detailed dietary changes that may occur during the programme. Gift vouchers will be offered to incentivise participation, and translators will be made available for any participants who wish to undertake an interview in another language.

*Analysis:* The longitudinal interviews will be analysed using the same methodology as for the NHS staff interviews in WP2. The individual dietary data will be auto-analysed within myfood24 and downloaded into Excel for group level analysis.

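### Incomplete interview series go to cross-sectional assessment, so the longitudinal strand rests only on participants who gave all three interviews

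*Protocol*

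**What the plan says.** Protocol, Work package 3, Stage 2 (Case study) sets one-to-one interviews "undertaken at the end of each phase of the programme (12,18 and 52 weeks"). It expects about 66 recruits. The group for repeated interviews is "at least 30 participants (10 from each delivery model) who start the programme and will be followed up over time"; a separate group of six or more is to come from non-starters and withdrawers. Attrition is met in two ways. The first is a larger sample: "We will aim to over sample in anticipation of some drop out". The second is a rule for incomplete series: "The interviews from participants who do not complete the longitudinal interviews will be assessed cross sectionally".

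The analysis paragraph of Stage 2 adds no rule for partial series. It refers to the thematic method of the Work package 2 staff interviews, which includes case-ordered matrices. The overview of Work package 3 explains why the design is longitudinal: "A longitudinal approach is deemed critical given the chronic relapsing nature of obesity, and the difficulties in long term weight loss maintenance".

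**The concern.** The longitudinal strand is there to show how experience changes within a person across diet replacement, food reintroduction and maintenance. The rule makes the full set of interviews the condition for entering it. Someone interviewed at weeks 12 and 18 but not at week 52 has given two linked accounts, yet these are assigned to cross-sectional assessment and the change between them drops out.

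The longest gap in the schedule runs from week 18 to week 52. That is 34 weeks, the whole maintenance phase, and it is the period to which the protocol's argument about relapse and weight maintenance applies most directly. If those who stop giving interviews differ from those who continue, the description of change over time reflects the latter. What is at stake is the interpretation of change; this qualitative strand has no effect estimate or error rate that could be affected.

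**Working it through.** The plan states no figure to reproduce. The check is a reading of the text, followed by simple arithmetic on labelled assumptions.

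**1. What counts as complete.** Stage 2 does not define it. Stage 3 lets participants keep their tablet if they complete all the longitudinal interviews. All three interviews is therefore the natural reading.

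**2. Whether a partial series is kept anywhere.** Stage 2 sends non-completers' interviews to cross-sectional assessment. Its analysis paragraph and the Work package 2 method make no exception for two interviews. Taken together, only full series remain in the longitudinal strand.

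**3. How many series could move.** The protocol gives no completion rate.
- On the minimum sample, with 20% to 50% missing at least one interview (assumed): 30 × 0.2 = 6 and 30 × 0.5 = 15 series, or 10 × 0.2 = 2 to 10 × 0.5 = 5 per delivery model. This counts incomplete series, not people who left the programme. Only those with two interviews hold within-person change that goes unused, so 6 to 15 is an upper limit on that loss under these rates.
- On the expected recruitment: 66 − 6 = 60 possible followed participants, assuming that everyone beyond the minimum six is followed. If the floor of 30 means completers (also assumed), 60 − 30 = 30 series, or 30/60 = 50%, could move to the cross-sectional set with the target still met.

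**4. Whether over-sampling helps.** Let p be the share of recruits doing well, c1 their completion rate and c0 the completion rate of the others. The share doing well among completers is p·c1 / (p·c1 + (1 − p)·c0). With p = 0.5 (assumed):

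| c1 | c0 | Share doing well among completers |
|---|---|---|
| 0.50 | 0.50 | 0.25 / 0.50 = 50% |
| 0.60 | 0.40 | 0.30 / 0.50 = 60% |
| 0.70 | 0.30 | 0.35 / 0.50 = 70% |

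The number recruited does not appear in the formula. A larger sample gives more full series with the same expected mix. If c1 and c0 are equal there is no distortion; if c0 exceeds c1 it runs the other way.

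**The case against.** The strongest objection is that missing an interview is not the same as leaving the programme or regaining weight. Nothing in Stage 2 ends a followed participant's interviews when they stop the programme. A leaver, or someone who regains weight, who gives all three interviews stays in the longitudinal set. A reader might infer that the strand will hold few or no leavers, or that relapse is removed from it. The documents do not support either inference. This part of the objection stands in full.

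Second, leavers' accounts are gathered elsewhere. Non-completers' interviews are kept, and further cross-sectional interviews may be added. At least six non-starters or withdrawers are sought, aimed equally at three discharge stages, which gives two per stage at the minimum. Stage 1 sends a survey at the point of withdrawal. The aim of learning what works and for whom is set for the interviews as a whole: "The purpose of the interviews is to provide in-depth insights into what works, for whom, in what context and why". It would be wrong to say that this evidence comes only from completers. This stands too, but these sources do not put a partial series back into the within-person analysis.

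Third, no separate within-person technique is specified, so the practical effect of the cross-sectional label is uncertain, and the team may intend to keep a person's transcripts linked. That is possible, but the text does not say so. This is also a stated rule, not a detail left open for a later analysis plan.

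**Conclusion.** The point holds for the longitudinal strand only. As written, that strand consists of participants with the full set of interviews, and change recorded in partial series is not used as change. This sits poorly with the protocol's own reason for choosing a longitudinal approach.

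The account of change over time is selective if completion is related to how participants fare. Neither the direction nor the size can be stated, because the protocol gives no completion rate; the counts and shares above illustrate the mechanism and are not forecasts. The conclusion rests on reading completion as all three interviews and on taking the cross-sectional rule at its word. It does not extend to a claim that non-completers' views are lost or that programme leavers will be absent. This is an inexpensive improvement to a qualitative component, not a threat to the evaluation as a whole.

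**What to change.** Replace the sentence in Stage 2 with: *All participants with two or more interviews are analysed longitudinally using every interview available; those with one interview are analysed cross-sectionally.*

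In the case-ordered matrices already planned under Work package 2, and carried over to these interviews, add two ordering variables: interview completion (full or partial series), and programme status (completed, or left, with the phase of leaving). Keeping them separate prevents a missed interview from being read as leaving the programme, and lets the two kinds of series be compared side by side.

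The cost is a change of protocol wording. The interviews are already scheduled, and no further data collection is needed. The one downside is that series of unequal length are somewhat harder to chart.
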